### **2.4 Additional Scientific Program**

- Genetic and molecular profiling of responders and non-responders (coordinated by [name], Kiel)

### **2.5 Extended Follow-up Phase (Register Phase)**

The GAZAI trial ends 30 months after the first Gazyvaro infusion for each individual patient. Further follow-up will be performed according to the standards of each participating center. The patients will

be asked to allow the transfer of this follow-up data to the trial center in Heidelberg to enable the collection and evaluation of long-time follow-up (PFS, OS, etc.) of this patient group.

### 3. TRIAL CONCEPT/ DESIGN

GAZAI is a prospective, open, nationally multi-center phase II trial for evaluation of LDRT in combination with Gazyvaro (Obinutuzumab) in patients with early stage nodal follicular lymphoma grade 1/2. Patients will get a completion of the “full” radiation dose in case of not reaching a sufficient response (metabolic CR *AND* morphologic PR/CR) after LDRT.

### 4. DURATION OF THE TRIAL AND EARLY STOPPING

#### 4.1 Duration and Time Line

The individual duration for each participant is 30 months. Patients may enter in a succeeding register phase without trial specific appointments or examinations.

##### Initial therapy phase: 3 months

Week 1-4 and week 8: 1 x weekly Gazyvaro (1000mg flat dose)

Week 9: Radiation therapy: 2x2 Gy *involved-site*

Week 12, 16: 1x weekly Gazyvaro (1000mg flat dose)

Week 18: Re-Staging (if applicable)

Week 20-23: Radiation therapy 18 x 2 Gy *involved-site* (if applicable)

##### Follow-up Phase: Month 6 – month 30 months (every 6 months)

The trial (FPI – LPO) will last approximately 5.5 years. The duration of patient recruitment is estimated with 3.5 years and starts in Q4 2017.

Length of the clinical phase:	5.5 years (66 months)
Start of trial preparation:	Q1 2015
FPI (First Patient In):	Q4 2017
LPI (Last Patient In):	Q1 2021
LPO (Last Patient Out):	Q3 2023
DBL (Data Base Lock):	Q1 2024
Completion of the statistical analysis:	Q2 2024
Completion of the trial report:	Q3 2024

#### 4.2 Early Stopping of the Trial or Early Stopping of a Trial Site

The trial can be stopped by the LKP if the DMC detects an unexpected accumulation of side effects (each grade 5, 2 succeeding grade 4 or 3 succeeding grade 3 CTC side effects), has new information about the effect-risk ratio of the investigated therapy or the used methods of examination. The trial can also be stopped by the LKP if recruitment is below the expectations and cannot be improved.

All investigators have to be informed immediately about a stopping or a permanent ending of the trial. The participating sites must accept the decision.

All study material has to be returned to the LKP in case of early stopping of the trial.

A participating site can also be closed early by the LKP if the site does not act according to ICH-GCP or according to the trial protocol or the recruitment or the quality of the data is below the expectations.

If the DMC suggests an interruption or an ending of the trial due to SAE evaluations or other reasons, the ethical board and the authorities (BOB and state authority) have to be informed. The Ethical Board and the authorities can also decide about an interruption or an ending of the trial.

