#### 1.5.1 Data Monitoring Committee (DMC)

The DMC consists of independent experts in the treatment of malignant lymphomas. The DMC should evaluate the conduct of the trial, the safety, and the achievements of the major endpoints. The duty of the DMC is to secure the ethically correct conduct of the trial and to protect the interests of safety for the patients.

The DMC will meet on a regular basis (GLSG annual meetings). The DMC will give recommendations to the LKP regarding modifications, stopping or continuation of the clinical trial. Those recommendations should be sent to the LKP in written form within 2 months after the meeting. The DMC will get the annual DSURs.

The members of the DMC are listed in the protocol.

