## 10.2 Period of Observation and Documentation

Adverse events (AEs) will be ascertained by the investigators using non-leading questions, noted as spontaneously reported by the patients to the medical staff or observed during any measurements on all study days. The observation period begins with the first administration of the Gazyvaro (before the first administration of the Gazyvaro: medical history) and ends with the last study visit, i.e. 30 month after the last take of study medication. AEs will be documented in the patient file and in the CRF. All subjects who present AEs, whether considered associated with the use of the trial medication/radiation therapy or not, will be monitored by the responsible investigator to determine their outcome; this applies to withdrawals too.

The end date of the SAE is defined typically the same as for AEs. The end date of the SAE must not be later than the end date of the corresponding AE.

AEs and SAEs that are on-going at the time of death are considered not resolved or resolving.

All SAEs and their relevance for the benefit/risk assessment of the study will be evaluated continuously during the study and for the final report. All SAEs will be documented in the "Serious Adverse Event" form.

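### The toxicity trigger in 4.2 depends on the DMC noticing one to three events, but the protocol states only annual DMC inputs and no route for SAEs to reach it in between

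*Combined protocol and SAP*

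**What the plan says.** Section 4.2 sets the toxicity rule: "The trial can be stopped by the LKP if the DMC detects an unexpected accumulation of side effects". The accumulation is specified in brackets as "each grade 5, 2 succeeding grade 4 or 3 succeeding grade 3 CTC side effects". The same section foresees the committee acting on serious events: "If the DMC suggests an interruption or an ending of the trial due to SAE evaluations or other reasons", the ethics committee and authorities must be told. It adds a separate power: "The Ethical Board and the authorities can also decide about an interruption or an ending of the trial".

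Section 1.5.1 gives the DMC's working rhythm and data. On meetings: "The DMC will meet on a regular basis (GLSG annual meetings"). On data: "The DMC will get the annual DSURs". Written recommendations may follow up to 2 months after a meeting.

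The safety reporting sections describe a different chain:

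- **10.2:** "All SAEs and their relevance for the benefit/risk assessment of the study will be evaluated continuously during the study". The evaluating body is not named. For adverse events in general, "AEs will be documented in the patient file and in the CRF".
- **10.3:** the investigator reports each SAE to the safety officer at the KKS within 24 hours.
- **10.4:** each SAE gets a second assessment, returned to the KKS within 48 hours. The LKP is named as second assessor, and the form includes a statement on benefit/risk. SUSARs go to the ethics committee, the competent authority and the investigators. A separate Safety Manual is cited for SUSAR reporting details.
- **10.1.8:** the investigator and the second assessor judge the relationship to treatment of each AE after Gazyvaro. No timing is given.
- **13.5:** SUSARs and changes in benefit/risk go to the ethics committee and the authority.

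The DMC is not named as a recipient in any of these reporting sections.

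**The concern.** A rule that can be met by a single death, two grade 4 events or three grade 3 events needs a data flow of matching speed to the body that applies it. The protocol assigns detection to the DMC and then states only annual contact for that body. Ad hoc contact is not barred, but it is not provided for either.

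What is at stake is the independence of the check. The LKP holds the stopping power under 4.2, is second assessor of SAEs under 10.4, and belongs to the steering committee, which under 1.5.2 decides on DMC recommendations. The DMC is described in 1.5.1 as made up of independent experts with the duty to protect patients. If it first learns of a met threshold at the next annual meeting, treatment of new patients may continue meanwhile on the LKP's judgement, subject to what the ethics committee and authority have been told.

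**Working it through.** **Step 1: compare the trigger with the stated inputs.**

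| Element | Stated in | Speed |
|---|---|---|
| Trigger: 1 grade 5, 2 grade 4 or 3 grade 3 | 4.2 | single events |
| DMC meetings | 1.5.1 | annual |
| DSURs to the DMC | 1.5.1 | annual |
| SAE to KKS | 10.3 | 24 h |
| Second assessment returned by the LKP | 10.4 | 48 h |
| SUSARs to ethics committee, authority, investigators | 10.4, 13.5 | expedited |
| Any SAE to the DMC | none stated | none stated |

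The route to the LKP takes about 24 h + 48 h = 72 h. For the DMC, the longest wait from a met threshold to the next stated contact is 12 months. If triggers fall evenly over the year, the average wait is 6 months.

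**Step 2: reproduce the number treated.** The protocol (11.1) expects 93 recruited, less about 15% for stage shift: 93 × 0.85 = 79.05, which agrees with the stated 79. Section 5.1 also uses 79 started on therapy as a stopping point for recruitment.

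**Step 3: patients started during the wait.** Recruitment is estimated at 3.5 years (4.1).

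- Rate: 79 / 3.5 = 22.6 per year.
- Average wait: 22.6 × 6/12 = 11.3, about 11 patients.
- Longest wait: 22.6 × 12/12 = 22.6, about 23 patients.

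**Step 4: sensitivity to the accrual rate.**

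- The milestones in 4.1 (first patient Q4 2017, last patient Q1 2021) imply roughly 3.25 years: 79 / 3.25 = 24.3 per year, so about 12 on average and 24 at most.
- Slower accrual, taking 55 treated over 3.5 years as an assumption: 55 / 3.5 = 15.7 per year, so about 8 on average and 16 at most.

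These counts are accrual over a waiting time. They apply only if a trigger occurs, accrual is even and nobody contacts the DMC between meetings. They say nothing about how likely a trigger is.

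**The case against.** The best defence is that other oversight is fast, and most of it stands. Every death is an SAE. Grade 4 is defined in 10.1.7 as life-threatening or disabling, which largely overlaps the SAE criteria, and symptom-free grade 4 laboratory values must be reconsidered for seriousness. So the grade 5 limb and most of the grade 4 limb reach the KKS within a day and the LKP soon after. The ethics committee and authority learn of SUSARs and benefit/risk changes and can halt the trial themselves. Adverse events of special interest enter the pharmacovigilance database even when non-serious, and under 6.5.4 a grade 4 or second grade 3 infusion reaction ends Gazyvaro for that patient.

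The rule is also discretionary: the trial can be stopped, and the accumulation must be unexpected. What counts as succeeding is not defined. Finally, the Safety Manual, or a DMC charter if one exists, may define a feed; neither was available. The manual is cited only for SUSARs, and the protocol mentions no charter.

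None of this supplies the DMC with events between meetings, so the mismatch between 4.2 and 1.5.1 remains. It does rule out three stronger inferences a reader might draw:

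- **That nobody would notice a run of non-serious grade 3 events.** Section 10.1.8 has the investigator and the second assessor evaluate each AE. That evaluation concerns causality and has no stated timing or cumulative count, but it is a stated process that puts these events before the person with the stopping power.
- **That the trial lacks timely safety oversight.** The SAE and SUSAR chain contradicts this.
- **That the threshold would probably be met between meetings.** With 23 patients a year, the chance of at least three patients with a severe infusion reaction is 0.47 at an 11% rate and 0.87 at 20%. But those rates (6.4.1) come from bendamustine and chlorambucil combinations in other populations, and such reactions are expected, so they need not count. If three consecutive patients are required, the yearly figures fall to about 0.02 and 0.13.

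**Conclusion.** The point holds as a mismatch between a stated rule and a stated schedule. Section 4.2 makes the toxicity trigger depend on DMC detection of one to three events, while the protocol gives the DMC annual contact only and leaves it off the SAE distribution. Followed literally, independent detection could lag by up to about 12 months, during which about 11 further patients would start on average and about 23 at most. This rests on 79 treated over 3.5 years, even accrual, triggers spread evenly over the year and no ad hoc contact.

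The size should not be read as a count of patients harmed or as a delay in all oversight: the LKP, and where applicable the ethics committee and authority, would know of serious events much sooner. Nor does meeting a threshold oblige anyone to stop. This is an inexpensive improvement to safety governance; it changes no estimate, sample size or analysis. Confidence is medium because the Safety Manual and any charter could already close the gap.

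**What to change.** Amend 1.5.1, 4.2 and 10.3 to 10.4 in two respects:

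1. The KKS safety officer forwards each death and each SAE of grade 3 or higher to the DMC chair on receipt.
2. The DMC holds an ad hoc review whenever a 4.2 threshold is met, rather than waiting for the annual meeting.

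If the Safety Manual or a DMC charter already provides for this, a cross-reference in 1.5.1 is enough.

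The cost is slightly more forwarding by the KKS, which already holds the reports, and more reading for the DMC. No patients, visits or procedures are added. A periodic listing of non-serious grade 3 and 4 events could be offered to the DMC as an option. It should not be required on this ground, because CRFs are on paper, entered twice and queried (12.1, 12.2), so repeated data cuts would take real effort.

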## 5. PARTICIPANTS

### 5.1 Number of Participants

As described in the chapter Sample Size Calculation, a maximum of 93 patients will be included in the trial.

The recruitment will be stopped, if (whatever occurs first)

- 79 patients will have a FDG-PET/CT confirmed stage I/II follicular lymphoma and a trial specific therapy has been initiated or
- 55 patients had a second restaging FDG-PET/CT in week 18 or
- 93 patients were included

Recruitment and treatment of the participating patients will be performed in 15 locations/30 sites (each location consists of a radiation oncology site and a hemato-oncology site).

The sites should have experience in the treatment of early stage follicular lymphoma (min. 5 patients / year). The sites should have the infrastructure for execution and documentation of a clinical trial according the AMG, Röntgenverordnung and Strahlenschutzverordnung. There must be the possibility to conduct a FDG-PET/CT.

Each location should include 6-7 patients. All sites, which successfully recruited and completely documented the therapy and follow-up of at least 4 patients will be considered for authorship in the final publication.

### 5.2 Common Criteria for Patient Selection

Patients ( $\geq 18$  yrs) with histologically proven and centrally histologically reviewed nodal follicular lymphoma grade 1 or grade 2 in the clinical stage I or II (Ann Arbor classification) should be included. The biopsy must be performed within the last 6 months and the complete staging must be within the last 4 months. A fine needle biopsy is not sufficient for a qualified diagnosis. The diagnosis must be centrally verified by one of the reference pathologists of the GLSG.

### Gender

According to the MIR data, no gender specific effects regarding the efficacy or the safety are anticipated. It is expected that the distribution of gender in the trial mirrors the natural distribution of the disease.

### 5.3 Inclusion Criteria

- Centrally reviewed CD20-positive follicular lymphoma grade 1/2 based on WHO classification (2008)
- Untreated (radiation-, chemo- or immunotherapy) nodal lymphoma (including involvement of Waldeyer's ring)
- Age:  $\geq 18$  years
- ECOG: 0-2

- Stage: clinical stage I or II (Ann Arbor classification)
- Risk profile: Largest diameter of the lymphoma  $\leq 7$  cm (sectional images)
- Written informed consent and willingness to cooperate during the course of the trial
- Adequate hematologic function (unless abnormalities are related to NHL), defined as follows: Hemoglobin  $\geq 9.0$  g/dL; absolute neutrophil count  $\geq 1.5 \times 10^9/L$ , Platelet count  $\geq 75 \times 10^9/L$
- Adequate bone marrow capacity: ANC  $\geq 1.5 \times 10^3/ml$ , thrombocytes  $\geq 100000 \times 10^3/ml$ , hemoglobin  $\geq 10$  g/dL
- Capability to understand the intention and the consequences of the clinical trial
- Adequate contraception for men and women of child-bearing age during therapy and 18 months thereafter
- Patients with non-active hepatitis B infection (HBsAg neg/HBcAB pos/HBV DNA neg) under 1-year prophylactic anti-viral therapy (e.g. Entecavir®) possible (see also 5.6. Prior and Concomitant Disease)

#### 5.4 Exclusion Criteria

- Extra nodal manifestation
- Secondary cancer in the patient's medical history (exclusion: basalioma, spinalioma, melanoma in situ, bladder cancer T1a, non-metastasized solid tumor in constant remission, which was diagnosed  $>3$  years ago)
- Concomitant diseases: congenital or acquired immune-deficiency syndromes, active infections including viral hepatitis (serology positive for HBsAg or HBcAb in combination positive HBV DNA), uncontrolled concomitant diseases including significant cardiovascular or pulmonary disease (see also 5.6. Prior and Concomitant Disease)
- Severe psychiatric disease
- Pregnancy / lactation
- Known hypersensitivity against Gazyvaro (Obinutuzumab) or drugs with similar chemical structure or any other additive of the pharmaceutical formula of the study drug
- Participation in another interventional trial or follow-up period of a competing trial which can influence the results of this current trial
- Creatinine  $> 1.5$  times the upper limit of normal (ULN) (unless creatinine clearance normal), or calculated creatinine clearance  $< 40$  mL/min
- AST or ALT  $> 2.5 \times$  ULN
- Total bilirubin  $\geq 1.5 \times$  ULN
- INR  $> 1.5 \times$  ULN
- PTT or aPTT  $> 1.5 \times$  the ULN

No patient must be included more than once.

#### 5.5 Criteria of Withdrawal

##### 5.5.1 Withdrawal of patients from treatment

Any patient can withdraw from the treatment at any time without personal disadvantages and without having to give a reason. Patients who discontinue participation in the clinical study on their own or patients who are withdrawn by the investigator, for reasons other than disease progression (i.e. in case of AEs, protocol violations, ...), will be defined as premature withdrawals. Premature withdrawals will not be replaced.

The investigator can also discontinue the study after considering the risk-to-benefit ratio, if he/she no longer considers the further treatment of the patient according to study protocol justifiable. The date of and the primary reason for the withdrawal, as well as the observations available at the time of withdrawal are to be documented on the CRF. Reasons leading to the withdrawal of a patient can include the following (**one primary reason must be determined**):

- **Lack of efficacy** of the study medication, e.g.
  - Progress of study disease compared to baseline
  - Need for a prohibited concomitant medication for the treatment of study disease
- **Intolerable adverse events**
- **Lack of patient's cooperation**, e.g.
  - Patient's request to withdraw
  - Lack of compliance, patient fails to attend the interim visits as agreed
  - Existing or intended pregnancy, lactation
- **Other reasons** (noting reason), e.g.
  - Other diagnosis than study disease
  - Did not meet major in-/exclusion criteria (coming to light after inclusion)

In all patients who finish the study prematurely, a withdrawal examination at least with respect to the primary endpoint should be carried out. The patient must be asked to consent to this last examination. The withdrawal examination must be documented in the CRF.

In case of a drop-out, all ongoing AEs or SAEs should be monitored until there are no more signs or symptoms or until the participant shows a stable condition.

### 5.5.2 Definition of drop-outs

Term	Definition
Drop-out, study	
Participation terminated completely, including follow-up
 
Possible reasons:
 
 
• Patient withdraws consent: Withdrawal
 
• Patient moved/cannot be contacted
 
• Follow-up-interventions cannot be performed due to medical reasons
 
• Non-compliance of patient
 
 
Drop-out after completion of study intervention: Lost to follow-up
 
FU-CRF-forms need to be marked as invalid.
 
Final examination will be performed, if patient agrees. Study-Completion/ Withdrawal-form will be completed.

Drop-out, study intervention	Termination of study intervention, follow-up as per protocol.
Screening-failure	
Exclusion criteria given prior to screening / enrolment:
 
Patient will be recorded at screening list, but will not be provided with a patient number.
 
(Depending on sponsor a screening CRF may have to be completed)

Protocol deviation	
Drop-out to study and drop-out to study intervention are both protocol deviations.
 
It needs to be predefined, how to manage each type of protocol deviation.
 
Major deviations:

If exclusion criteria become evident after enrolment, and safety of the participant is affected, or if the diagnosis does not any more relate to the indication listed in the protocol affecting the benefit/risk negatively, the participant has to be excluded from study intervention. FU-examinations may still be performed.

Minor deviations:

Other protocol deviations (errors in timing of visits/ missing samples/ missing examinations) do not result in exclusion

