## 9. FOLLOW-UP AND POSSIBLE TREATMENTS AFTER END OF TRIAL

Follow-up procedures and possible further treatments after the trial (early ending or after month 30) should be performed according to local standard procedures at each site. The results of this extended follow-up should be collected with the consent of the patient as in a register. It is the goal to analyze these long time follow-up data retrospectively in the future.

**In case of a recurrence at the primary involved site after 2x2 Gy, it should be respected, that a "full dose" up to the target dose of the MIR trial (40 Gy) should still be possible.**

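### Section 5.5.2 lets medical inability or non-compliance end trial follow-up, and no later vital or progression status is collected, so Kaplan-Meier 2-year PFS and OS may be biased upward

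*Combined protocol and SAP*

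**What the plan says.** Section 5.5.2 separates two kinds of drop-out. For a study drop-out the consequence is "Participation terminated completely, including follow-up". The possible reasons listed are withdrawal of consent, a patient who has moved or cannot be reached, "Follow-up-interventions cannot be performed due to medical reasons", and non-compliance. For these patients "FU-CRF-forms need to be marked as invalid", and "Final examination will be performed, if patient agrees".

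For a drop-out from study intervention the rule is "Termination of study intervention, follow-up as per protocol". Further down, under major deviations, a participant who must be excluded from study intervention (an exclusion criterion found after enrolment that affects safety, or a diagnosis that no longer fits the indication) is covered by "FU-examinations may still be performed". The section also says of deviations: "It needs to be predefined, how to manage each type of protocol deviation".

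The endpoints affected are 2-year PFS and OS of all treated patients (sections 2.3 and 11.2), estimated by Kaplan-Meier with Greenwood intervals in the ITT and PP populations (section 11.4). Section 11.3 puts everyone who received at least part of the treatment in the ITT and safety populations. Section 11.6 defines PFS and OS but gives no censoring rule.

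**The concern.** Learning that a patient has died needs no study procedure. Nor does learning from the treating physician that the lymphoma has relapsed. Yet inability to undergo follow-up procedures is listed as a possible ground for ending participation altogether. Kaplan-Meier treats a patient who leaves as having the same future risk as those who stay. Patients who leave because they are medically unfit may well have a higher risk, and then both curves sit too high.

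This matters even in a descriptive trial. Section 1.3 accepts a remaining risk of late in-field recurrence in exchange for much less radiation, and PFS is one of the endpoints where that exchange is measured. New late events would also be missed, because section 5.5.1 follows only adverse events already ongoing at drop-out. Section 6.4 names late-onset neutropenia and hepatitis B reactivation as risks.

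The second issue is one of consistency. A dosed patient excluded after enrolment is off study intervention and is analysed as ITT, yet one row requires follow-up and the other leaves it optional.

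**Working it through.** **What is collected after a study drop-out**

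- Ongoing AEs and SAEs are followed until resolved or stable, including in withdrawn patients (sections 5.5.1, 10.1.8, 10.2). A fatal outcome of such an event would be recorded. Later deaths and new events would not.
- A withdrawal examination should be done, at least for the primary endpoint (section 5.5.1), which is week-18 metabolic CR. It is a single visit and needs the patient's consent.
- Progression under treatment need not be reported as an AE (section 10.1.2), although section 10.1.1 lists recurrence among possible AEs. AE reporting is therefore not a dependable source for PFS.
- After early ending, section 9 says "Follow-up procedures and possible further treatments after the trial (early ending or after month 30) should be performed according to local standard procedures". Those results are gathered as in a register, with consent separate from trial consent (section 13.3).

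No section asks for vital or progression status at the scheduled times after study drop-out.

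**Plan figures used**

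The protocol gives no sample-size or precision figure for PFS or OS. The recruitment chain in section 11.1 reproduces: 93 × 0.85 = 79.05 (stated 79), 79 × 0.70 = 55.3 (stated 55), 55 × 0.90 = 49.5 (stated 50). The plan applies its 10% drop-out to the 55 patients assessed at week 18. Using 10% of the 79 treated over two years (about 8 patients) is my assumption.

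**Size of the possible bias**

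Inputs: base 2-year PFS S = 86% (the MIR result in section 1.1.5), base OS S = 97% (assumed), a fraction d leaving for medical reasons, exits uniform over 24 months, constant hazards, and a post-exit hazard HR times the base hazard.

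Everyone has the base hazard while observed, so Kaplan-Meier returns S. Put H = −ln S and a = (HR − 1) × H. The leavers' true 2-year rate is S × (1 − e^(−a))/a, so

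overstatement = d × S × [1 − (1 − e^(−a))/a].

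Worked case, PFS, d = 0.10, HR = 10: H = 0.1508, a = 1.357, (1 − 0.257)/1.357 = 0.547, overstatement = 0.10 × 0.86 × 0.453 = 0.039, or 3.9 points. A simulation of 400,000 patients gave the same figure.

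| Overstatement, points | HR 1 | HR 2 | HR 5 | HR 10 |
|---|---|---|---|---|
| PFS, 5% leave | 0 | 0.3 | 1.1 | 1.9 |
| PFS, 10% leave | 0 | 0.6 | 2.1 | 3.9 |
| PFS, 15% leave | 0 | 0.9 | 3.2 | 5.8 |
| OS, 10% leave | 0 | 0.1 | 0.6 | 1.2 |

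**Bounds for PFS**, with 8 of 79 lost and 86% of the other 71 event-free (61.06 patients): if all 8 have an event, 61.06/79 = 77.3%; if none does, 69.06/79 = 87.4%.

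**Sampling error for scale:** 1.96 × √(0.86 × 0.14/79) = 0.077, or ±7.7 points.

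**The case against.** A reader might infer that every patient unfit for a follow-up procedure is removed from the trial. The text does not say so. The table lists possible reasons, and the same section classes missed examinations as minor deviations that do not lead to exclusion. A patient who merely cannot have a contrast CT is a poor example, because follow-up imaging may be CT or MRI (section 8.1.5), section 8.1.1 lets FDG-PET/CT replace either, and contrast is not mandatory for the CT part of PET/CT (section 8.2). This stands. The rule permits loss of follow-up; it does not compel it.

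A reader might also infer that PFS and OS are informatively censored as a matter of fact. The protocol gives no rate of medical drop-out and no censoring rule, and it leaves procedures to a SAP finalised before database lock. So this is a risk, and it vanishes if the leavers' hazard is unchanged. But a later SAP cannot recover data that were never collected.

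A large effect, especially on OS, is tempting but extreme. Suppose 8 of 79 are censored at the start and 2 of them die: true OS is 77 × 0.97/79 = 94.5%. That already implies leaver survival of 0.75 × 0.97 = 72.8%, a hazard ratio of ln 0.728/ln 0.97, about 10.

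The difference between required and optional follow-up shows that follow-up can be incomplete and vary by site. By itself it does not show that loss is related to prognosis. Voiding the follow-up forms may mean no more than cancelling unused paper pages; nothing says that data already collected are discarded.

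Finally, PFS and OS are secondary, no hypothesis is tested, and the historical comparison with MIR named in section 2.1 covers week-7 morphologic response and quality of life.

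**Conclusion.** The point holds as a risk of bias created by a data-collection rule. Section 5.5.2 allows medical inability or non-compliance to end scheduled follow-up, and the remaining safeguards do not supply later vital or progression status. Kaplan-Meier 2-year PFS and OS may therefore be too high. With 10% of 79 leaving for medical reasons, exits spread over 24 months and a post-exit hazard ratio of 1 to 10, the overstatement is about 0 to 4 points for PFS and 0 to about 1 point for OS. All of these inputs are assumptions except the 79 and the 86% historical PFS. The 77.3% figure is only a worst-case bound. In most scenarios the bias is well below the ±7.7-point sampling error, but unlike sampling error it runs in one direction when leavers do worse.

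Separately, the two follow-up statements for patients taken off study intervention conflict for dosed patients and must be reconciled. The week-18 primary endpoint is not at issue here. This is a cheap improvement worth making and does not threaten the trial's main result.

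**What to change.** In section 5.5.2:

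- Limit study drop-out to withdrawal of consent to further data collection and to patients who cannot be traced.
- For medical reasons or non-compliance, omit the procedures that cannot be done but keep the follow-up forms valid. At the scheduled follow-up times (months 6 to 30), record vital status, known progression, new lymphoma therapy and SAEs from the treating physician or by telephone.
- Apply at least this status follow-up to every patient who received a dose, and reconcile the two statements on follow-up after exclusion from study intervention.

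The SAP should then state the PFS and OS censoring rules that section 11.6 lacks.

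Cost: protocol wording, plus a few calls and a short status entry per affected patient (perhaps 8 on the assumption above). No extra scan or visit is needed, and withdrawn consent is still respected.
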